### Design:

- This is a single-institution, open-label, non-randomized 3 + 3 design phase I dose-escalation study.
- Groups of 3 to 6 subjects will receive CIV rhIL-15 at doses of 0.1, 0.25, 0.5, 1, 2, and 4 mcg/kg/day for 10 days provided that DLT has not been observed.

**Abbreviated Title:** *Ph I Study of CIV rhIL-15*

**Version Date:** 06/13/2018

- After assessments of the 10-day dosing cohorts have been completed, new groups of 3 to 6 subjects will receive CIVrhIL-15 at doses of 3, 4 and 5 mcg/kg/day for 5 days provided that a DLT has not been observed.
- Patients with evidence of response and the absence of significant toxicities will be eligible for repeat cycles of treatment.
- Samples for correlative studies will be obtained prior to treatment and at specific times points during and after treatment to assess pharmacokinetics of rhIL-15, the effect of rhIL-15 on immune cell subset populations and pro-inflammatory cytokine levels in the peripheral blood and for the development of neutralizing anti-rhIL-15 antibodies.

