#### 1.2.1.4 Clinical Experience from the Completed IV Bolus Phase I Study

The first in-human (FIH) trial that tested a daily 30-minute infusion (IVB) for 12 days in subjects with metastatic melanoma and renal cell cancer has been completed after treating 18 subjects (58). Doses assessed in this trial were 3, 1 and 0.3  $\mu\text{g}/\text{kg}$ ; with the 0.3  $\mu\text{g}/\text{kg}$  dose determined to be the MTD for this schedule. DLTs at the 3  $\mu\text{g}/\text{kg}$  dose were grade 3 hypotension and grade 3 thrombocytopenia; DLTs at the 1  $\mu\text{g}/\text{kg}$  dose were grade 3 elevations of transaminases. One Serious Adverse Event (SAE) grade 3 pneumonitis possibly related to rhIL-15 treatment occurred during a subject's second cycle of treatment. The frequency and severity of common cytokine related toxicities such as fever, rigors, capillary leak syndrome and edema were generally proportional to the dose of rhIL-15. Abnormal laboratory results were seen in all subjects and most often were CTC grade 1 or 2 events. Laboratory adverse events (AEs) were less clearly proportional to the dose of rhIL-15 both in frequency and severity as indicated by low and transient occurrence of grade 2 laboratory AEs in the 3  $\mu\text{g}/\text{kg}$  cohort, whereas both DLTs in the 1  $\mu\text{g}/\text{kg}$  dosing cohort were elevated AST/ALT. The 0.3  $\mu\text{g}/\text{kg}$  dosing cohort also had a high frequency of laboratory abnormalities including non-DLT grade 3 elevation of ALT/AST in one patient. There was a consistent temporal pattern of post-treatment AEs most clearly seen in 3  $\mu\text{g}/\text{kg}$  cohort with fever beginning approximately 2 to 2½ hours after the rhIL-15 infusions, then rigors followed almost immediately by decreased blood pressure (BP).

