### 3.2.1 DLT will be defined as follows:

Grade 2 diarrhea lasting more than 24 hours or any grade 3 or 4 toxicity, if deemed possibly, probably or definitely related to the study drug by the PI during the first cycle of treatment, **with the following exceptions:**

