### **3.5 DOSE MODIFICATIONS**

Since this is a phase I study intending to define the MTD, there will be no dose modifications or interruption of treatment during the first cycle of treatment for the 5-day dosing cohorts. **The rhIL-15 infusion maybe interrupted for up to 24 consecutive hours for reasons other than DLTs without bearing on the patient's continued treatment during subsequent treatment cycles for patients treated with either schedule. Interruptions of the infusion will not be made up by extending the 240- or 120-hour infusion and there will be no change in the date and time the 10- or 5-day infusion is terminated unless the treatment is stopped early for safety reasons.** Patients with evidence of clinical benefit at restaging may have interruptions or early termination of their CIV rhIL-15 during later retreatment cycles for non-DLT events to improve tolerability of the treatment without forfeiting the possibility of subsequent treatment cycles. Stoppage of less than 15 minutes occurring during the daily change of the rhIL-15 infusion device will not be considered an interruption.

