#### **3.10.1 Off-Treatment Criteria**

- DLT as defined in Section [3.2](#).
- Persistent (> 14 days) treatment-related grade 2 (non-DLT) adverse events.
- Completion of protocol therapy
- Patient requests to be withdrawn from active therapy.
- Disease progression.
- No evidence of clinical response (i.e., patient has stable disease) on radiographic restaging after 2 consecutive cycles of treatment.
- The detection of anti-IL-15 neutralizing antibody serum titer  $\geq 500$  ng/mL as described in [APPENDIX C](#) prior to subsequent treatment cycles.
- Evidence the patient has developed auto-immunity that involves a vital organ (heart, kidney, brain, eye, thyroid or adrenal gland, colon, lung). Patients who develop new auto-antibodies without clinical evidence of end organ dysfunction will be seen by the appropriate Internal Medicine subspecialists to assess their risk for developing an autoimmune syndrome.
- Interruption of CIV rhIL-15 treatment for any reason for more than 24 consecutive hours during cycle 1. Stoppage of less than 15 minutes occurring during the daily change of the rhIL-15 infusion device will not be considered an interruption.
- Positive pregnancy test

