The MTD for each schedule will be based on the assessment of DLT during the first cycle of treatment, and will be defined as the dose level at which less than one-third of patients (0/3 or 0-1/6 patients) treated at that dose experience a DLT, with the next higher dose level demonstrating a one-third or greater number of patients ( $\geq 2/3$  or  $\geq 2/6$  patients) having DLT. If a patient did not experience DLT and did not finish 1 cycle of treatment (either 42 or 21 days), he or she will not be evaluable for determination of the MTD and will be replaced in the dose level. An additional 3 to 6 patients will be enrolled at the MTD or, if no severe or dose-limiting toxicities are encountered, the maximum administered dose of rhIL-15, so that a total of 9 patients will potentially be treated at MTD for either schedule to better characterize the clinical activity of

CIV rhIL-15 in this patient population. If feasible, the patients enrolled in this expansion cohort will be limited to histologic cancer subtypes previously shown to be sensitive to immunotherapy (renal cell carcinoma, melanoma, prostate, colorectal and ovarian cancer).

As of April 2016, twenty-four evaluable patients have enrolled on Dose Levels 1-6; with 2 more to be enrolled in Dose Level 6 after Amendment G. A maximum of 6 evaluable patients may be enrolled at DL 7 & 8 with an additional 9 at DL 9. If all dose levels are evaluated (with 6 patients per remaining dose levels and 9 total patients at the MTD or maximum administered dose), a maximum of 47 evaluable patients will be enrolled. An additional 5 patients may be enrolled to compensate for inevaluable patients; thus, bringing the maximum accrual ceiling to 52.

Similarly, if all dose levels are evaluated, the minimum number of patients required will be 41 (24 evaluable patients have enrolled at DL 1-6; with 2 more to be enrolled in Dose Level 6 after Amendment G and with 3 patients enrolled at DL 7 & 8; 9 at DL 9; and 5 inevaluable patients a minimum of 46 will be reached).

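### After cycle 1, a related grade 3 or 4 event meets no off-treatment criterion by grade and relatedness, while a related grade 2 event lasting more than 14 days does

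*Combined protocol and SAP*

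**What the plan says.** - **DLT definition (3.2.1).** Two kinds of toxicity qualify by severity: those of grade 3 or 4, and diarrhea of grade 2 that persists beyond 24 hours. Such an event counts as a DLT "if deemed possibly, probably or definitely related to the study drug by the PI during the first cycle of treatment". Hematologic and non-hematologic exceptions follow, and several of them add that rhIL-15 will be continued.
- **Statistical section (8).** It uses the same window: "The MTD for each schedule will be based on the assessment of DLT during the first cycle of treatment".
- **Off-treatment list (3.10.1).** Severe toxicity enters only through "DLT as defined in Section" 3.2. The next bullet is "Persistent (> 14 days) treatment-related grade 2 (non-DLT) adverse events". The other safety-related bullets are vital-organ autoimmunity, a neutralizing-antibody titer, an interruption of more than 24 hours in cycle 1, and a positive pregnancy test.
- **Dose modifications (3.5).** Patients with clinical benefit may have the infusion interrupted or ended early "during later retreatment cycles for non-DLT events to improve tolerability of the treatment" and still receive further cycles.
- **Précis, Design.** "Patients with evidence of response and the absence of significant toxicities will be eligible for repeat cycles of treatment". It does not say which toxicities are significant.
- **Treatment after cycle 1 (3.1).** Patients on the 10-day schedule stop if there is no ongoing response after any 2 consecutive cycles. Patients on the 5-day schedule have 4 cycles to show responsiveness. Responders on either schedule may continue.

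**The concern.** One definition is doing two jobs. For the MTD tally, a DLT limited to cycle 1 is usual and clear. For taking a patient off treatment, the rule has to work in every cycle, and the cross-reference brings the cycle-1 limit with it. After cycle 1 the written list then reacts to a long grade 2 event but not, by its grade and attribution, to a grade 3 or 4 event.

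At stake is a basic safety rule, in a trial whose 5-day schedule is still seeking an MTD and gives patients several cycles. Severe toxicity after cycle 1 has been seen with this agent: Section 1.2.1.4 reports, in the bolus trial of 18 subjects, a serious adverse event in which "grade 3 pneumonitis possibly related to rhIL-15 treatment occurred during a" subject's second cycle. Without a written rule, similar later-cycle events could be handled differently from one patient to the next.

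**Working it through.** The question is textual, so the check sets the sections side by side.

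**Step 1. Is the cycle-1 limit really part of the definition?** In 3.2.1 the phrase could be parsed as saying only when the investigator makes the attribution. Section 8 settles it, because it bases the MTD on DLT in the first cycle.

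**Step 2. Apply 3.2.1 and 3.10.1 together to related events.**

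| Related event | Cycle 1 | Cycle 2 or later |
|---|---|---|
| Grade 3 or 4, no listed exception | DLT, so off treatment | Not a DLT; no bullet met by grade and relatedness |
| Grade 2 diarrhea, more than 24 hours but not more than 14 days | DLT, so off treatment | Not a DLT and too short for the grade 2 bullet |
| Grade 2, more than 14 days | Off treatment | Off treatment |

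In the right-hand column the only row leading to removal is the grade 2 row.

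**Step 3. Compare with 3.5.** Two phrases there use the term DLT.
- The first allows interruptions of up to 24 hours for reasons other than DLTs and mentions subsequent cycles. It is ambiguous: the reference to subsequent cycles can attach to the patient's continued treatment, in which case the interruption itself may fall in cycle 1.
- The second, "during later retreatment cycles for non-DLT events to improve tolerability of the treatment", is placed squarely in later cycles. Setting non-DLT events apart there implies that DLTs can also occur there. Under 3.2.1 every later-cycle event is non-DLT, so the qualifier would exclude nothing.

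**Step 4. The exceptions in 3.2.1.** The statements that rhIL-15 will be continued are written as exceptions to the cycle-1 definition. The protocol does not say whether they apply in later cycles.

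**Step 5. How many cycles are concerned?** Inputs are from 3.1.
- 5-day schedule: 4 cycles to show responsiveness, of which cycles 2 to 4 lie outside the DLT window: (4 − 1)/4 = 3/4.
- 10-day schedule: 2 cycles before the response decision: (2 − 1)/2 = 1/2, plus any continuation cycles.

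**Step 6. Are the trial's statistics affected?** The figures that depend on the DLT rate are the escalation probabilities in Section 8. With true DLT rate p, escalation follows 0 of 3, or 1 of 3 and then 0 of 3:

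P(escalate) = (1 − p)³ + 3p(1 − p)² × (1 − p)³

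| p | 10% | 20% | 30% | 40% | 50% | 60% |
|---|---|---|---|---|---|---|
| Section 8 | .91 | .71 | .49 | .31 | .17 | .08 |
| Recomputed | .906 | .709 | .494 | .309 | .172 | .082 |

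For example, at p = 0.5: 0.125 + 0.375 × 0.125 = 0.172. The table reproduces. It rests on cycle-1 DLTs only, so clarifying the later-cycle rule does not change it.

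**The case against.** The strongest reply is that patients are not left unprotected.
- The vital-organ autoimmunity bullet in 3.10.1 applies in any cycle and names the lung. The pneumonitis case, if judged autoimmune, would fall under it. That case also came from the bolus schedule, so it shows that severe later-cycle events occur with this agent, not that this one would go uncovered.
- Section 3.10.2 lets the investigator take a patient off study for a new medical condition that makes continuing unsafe.
- Sections 3.1 and 3.5 refer to patients who stop because of toxicity and to infusions stopped early for safety.
- The Précis makes repeat cycles conditional on toxicity. Section 3.1 and the study calendars do not grant the 7 extra days for recovery from treatment-related toxicity.
- One research team discusses each patient weekly (7.4.1) and would probably read DLT as applying in any cycle.

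All of this stands as far as it goes, so it would be wrong to infer that a severe later-cycle event cannot lead to stopping. But none of these texts gives a grade and attribution threshold for later cycles. Autoimmunity covers one class of event. The off-study rule is discretionary and takes the patient off study, not just off treatment. The Précis wording is undefined and is not carried into 3.10.1. If the team does read DLT as applying in any cycle, the written definition does not say what is meant.

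A reader might also infer three further things that the documents do not support.
- **That sites will diverge.** The trial is single-institution; what remains is possible inconsistency between patients.
- **That the primary objective is blurred.** The MTD window is the same in 3.2.1 and Section 8. Toxicity is graded by CTCAE 4.0 (6.3), all patients are evaluable from first treatment (6.2.2.1), and related grade 3 and 4 events are tabulated without a cycle limit (7.2.2).
- **That three quarters of the toxicity risk is uncovered.** The 3/4 counts cycles, not patients or events.

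**Conclusion.** The point holds as a wording defect in a safety rule, and it should be corrected. Read literally, 3.2.1 and 3.10.1 leave a related grade 3 or 4 event after cycle 1 with no off-treatment criterion triggered by grade and relatedness, while a related grade 2 event lasting more than 14 days has one. Section 3.5 implies a different understanding of when DLTs can occur. This is a tension between the sections, resting on one clear phrase and one ambiguous one, not a flat contradiction.

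The reach is every cycle after the first on both schedules. The documents give no rate of later-cycle severe events, so the number of patients affected cannot be estimated. The conclusion assumes that the cross-reference in 3.10.1 carries over the whole definition, window included, as its wording says. The effect on the MTD, the escalation rule and the toxicity-profile analysis is nil.

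**What to change.** 1. In 3.2.1, state that the first-cycle window applies to the MTD and escalation tally.
2. In 3.10.1, replace reliance on the cross-reference alone with a separate, explicit statement of how related events that meet the 3.2.1 severity terms are handled in cycle 2 and later, including whether the listed exceptions apply there.
3. Reconcile the following so that they give one answer for such an event: Précis (Design), 3.1, 3.2.1 with its exceptions, 3.5, the cycle-length notes in 3.8.1 and 3.8.2, 3.10.1 and 3.10.2.

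What the rule should be is a clinical decision for the sponsor and investigators; the point here is only that the text must state one.

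The cost is a protocol amendment to wording. The wording change itself needs no extra patients or visits and no new analyses, and Section 8 keeps its MTD and escalation rules.

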#### **Hematologic exceptions:**

- Grade 3 or 4 lymphopenia
  - rhIL-15 will be continued in the event of asymptomatic grade 3 or 4 lymphopenia, unless there are clinical signs of significant infection (persistent fevers, labile blood pressure, localized complaints or findings on physical exam, hypoxia or organ dysfunction).
- Grade 3 granulocytopenia
  - rhIL-15 will be continued in the event of grade 3 granulocytopenia unless there are clinical signs indicating a significant infection, as listed above.
- Grade 3 leukocytosis (WBC  $> 100,000/\text{mm}^3$ ) in the absence of signs of leukostasis or other toxicities possibly related to the expansion of activated cells.

#### **Non-hematologic exceptions:**

- Transient (< 24 hours) grade 3 hypoalbuminemia, hypokalemia, hypomagnesemia, hyponatremia or hypophosphatemia which responds to medical intervention. rhIL-15 will be continued while the metabolic abnormalities are corrected by intravenous and oral supplementation.
- Non-sustained (< 7 days) grade 3 liver function test (ALT, AST, alkaline phosphatase, total or direct bilirubin) abnormalities in the absence of clinical signs of hepatic dysfunction (lethargy, confusion, anorexia, pruritus, tremor). rhIL-15 will be continued as long as these abnormalities do not persist more than 7 days or the patient does not exhibit findings consistent with hepatic toxicity.

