### **3.3 DOSE ESCALATION**

Dose escalation will proceed in cohorts of 3 to 6 patients. Patients will not begin treatment at the next higher dose level until all patients treated at the previous dose level have reached day 21 of the protocol, recovered from any clinical or laboratory toxicities and would be able to initiate another cycle of treatment unless restaging has demonstrated progression of their disease). The MTD is the dose level at which no more than 1 of up to 6 patients experience DLT, and the dose below that at which at least 2 (of  $\leq$  6) patients have DLT as a result of the drug. If a patient did not experience DLT and did not finish 1 cycle of treatment (42 days), he or she will not be evaluable for determination of the MTD and will be replaced in the dose level.

Dose escalation will follow the rules outlined in the Table below.

Number of Patients with DLT at a Given Dose Level	Escalation Decision Rule
0 out of 3	Enter up to 3 patients at the next dose level
$\geq 2$	Dose escalation will be stopped. This dose level will be declared the maximally administered dose (highest dose administered). Up to 3 additional patients will be entered at the next lowest dose level if only 3 patients were treated previously at that dose.
1 out of 3	Enter up to 3 more patients at this dose level. 

• If 0 of these 3 patients experience DLT, proceed to the next dose level.

• If 1 or more of this group suffer DLT, then dose escalation is stopped, and this dose is declared the maximally administered dose. Up to 3 additional patients will be entered at the next lowest dose level if only 3 patients were treated previously at that dose.

$\leq 1$ out of 6 at highest dose level below the maximally administered dose	This is the MTD and is generally the recommended phase 2 dose. At least 6 patients must be entered at the recommended phase 2 dose.

The MTD has already been defined for patients treated with the 10-day regimen. For patients treated with the 5-day regimen dose escalation will continue through the 5 mcg/kg/day dose level in the absence of  $\geq 2$  DLTs for the patients treated for any of the dose levels being evaluated for the 5-day regimen. If an MTD is not identified up to 9 patients may be treated at the maximum administered dose (MAD) of 5 mcg/kg/day to better evaluate the therapeutic potential of rhIL-15 given by this schedule.

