### **3.4 DRUG ADMINISTRATION**

For all dose levels, the dose of rhIL-15 will be diluted in the appropriate volume of 0.1% human serum albumin (HSA) in 5% dextrose in water, USP (D5W) to reach a final rhIL-15 concentration of 1 mcg/mL. The rhIL-15 treatment will be administered to the patient by continuous 24-hour intravenous infusion (CIV) using portable ambulatory pump on the inpatient unit for either a total of 240 or 120 hours depending on the treatment cohort. Treatment with rhIL-15 will begin within 4 hours of preparation of the infusion bag and each infusion bag must be completed within 24 hours from the time drug administration begins. If the infusion bag is not empty at the 24-hour time point, the remaining solution will be discarded and the next infusion bag will be started. **The 240- or 120-hour infusion time frame will not be extended.**

The rhIL-15 infusion solution is stable at a concentration of 1 mcg/mL with 0.1% HSA for 4 hours at controlled room temperature (15°C–30°C) prior to initiation of the 24-hour infusion or 24 hours at 2-8° C prior to initiation of the 24-hour infusion. This stability information was previously documented by the Biopharmaceutical Development Program (BDP) of Leidos Biomedical Research, Inc.-Frederick, the drug manufacturer.

The rhIL-15 will be infused through a PICC or another appropriate CVAD.

Samples for PK assessments must **not** be drawn from the PICC or CVAD through which the rhIL-15 is infused. If feasible, venous access will be placed at 2 locations **NOT in the same extremity** during cycle 1. This will prevent contamination of the blood draws with residual rhIL-15 present in the catheter or double lumen catheters with distal openings in close proximity.

In Cycle 2 and beyond, the IL-15 infusion may be put on hold for 5-15 mins to collect routine (non-PK) daily labs.

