### 3.8.2 5 Day Schedule

Procedure	Pre-treatment		Days During-treatment 							After treatment			
	Screening	Baseline 	1	2	3	4	5	6	8	21±4 	End of Treatment 	Follow-Up Period 	End of Study 
CIV rhIL-15 treatment 			x	x	x	x	x	x 					
Pathology confirmed	x												
Performance status	x	x	x						x		x	x	x
History & physical exam 	x	x	x	x	x	x	x	x	x		x	x	x
Vital Signs  and Weight	x	x	x	x	x	x	x	x	x		x	x	x
NIH Advance Directives Form 													
Acute Care, Hepatic and Mineral Panels and LDH	x	x	x	x	x	x	x	x	x	x	x	x	x
Ammonia level	x		x						x				
I/Os			x	x	x	x	x	x	x				
CBC w/differential	x	x	x	x	x	x	x	x	x	x	x	x	x
Reticulocyte Count		x											
Hepatitis and HIV serology	x												
Thyroid function tests: TSH and T4	x									x	x		
Troponin T or I, based on availability of test in DLM		x	x										
Urinalysis	x												
EKG	x		x										
Pulmonary function tests	x												
HLA (A, B, C, DR, DQ) typing		x											
Tumor imaging and serum tumor markers 	x	x									x		
Serum βHCG 	x		x										
ANA, RF and anti-thyroid antibodies	x										x		
Pharmacokinetics (PK) 			x	x	x	x	x	x					
Serum immunoglobulin levels		x											
Flow cytometry ([name] Lab) 		x	x						x	x			
Flow cytometry ([name] Lab) 		x	x						x	x			
Cytokine and MesoScale inflammatory cytokines 			x	x	x	x	x	x	x	x			
Anti-IL-15 antibodies 			x							x		x	
Optional Tumor Biopsies 		x							x				

**Abbreviated Title:** Ph I Study of CIV rhIL-15

**Version Date:** 06/13/2018

1. All cycles are 21 days in length, but the end of cycle evaluations may be performed  $\pm$  4 days from this time point and an additional 7 days allowed for reasons other than recovery for treatment-related toxicities. Cycle 1 day 21 and cycle 2 day 1 maybe the same calendar day for certain patients. This also applies to later cycles where day 21 of a previous cycle falls on the same calendar day as day 1 of the subsequent cycle.
2. Patients whose best response after 4 consecutive cycles of treatment is stable disease will be followed with routine exams and restaging scans: Every 60 days x 3; then quarterly for up to 2 years after starting treatment unless progressive disease is documented, or they begin another treatment for their cancer.

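### Liver-test exception in Section 3.2.1: the dosing sentence joins its two conditions with 'or' where the DLT exemption requires both, a minor contradiction that bites during the 120-hour infusion

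*Combined protocol and SAP*

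**What the plan says.** Section 3.2.1 counts related grade 3 or 4 toxicities as DLTs, "if deemed possibly, probably or definitely related to the study drug by the PI during the first cycle of treatment", and then lists exceptions. The liver-test bullet, under the non-hematologic exceptions, has two sentences.

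- **Sentence 1 (DLT status).** It exempts grade 3 ALT, AST, alkaline phosphatase or bilirubin results that last < 7 days, and only "abnormalities in the absence of clinical signs of hepatic dysfunction". It gives lethargy, confusion, anorexia, pruritus and tremor as the signs.
- **Sentence 2 (dosing).** "rhIL-15 will be continued as long as these abnormalities do not persist more than 7 days or the patient does not exhibit findings" of hepatic toxicity.

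Other sections set the context:

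- Section 3.3: "The MTD has already been defined for patients treated with the 10-day regimen". The remaining dose finding is on the 5-day schedule.
- Section 3.4: "The 240- or 120-hour infusion time frame will not be extended".
- Section 3.5: "there will be no dose modifications or interruption of treatment during the first cycle of treatment for the 5-day dosing cohorts". The same section says the end time of the infusion is fixed "unless the treatment is stopped early for safety reasons".
- Section 3.10.1 lists a DLT as a reason to come off treatment.

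**The concern.** Sentence 1 needs both conditions; sentence 2 needs only one. A patient on the 5-day schedule who develops a grade 3 liver-test rise with, say, confusion or tremor fails sentence 1, yet sentence 2 as worded says to carry on.

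Sentence 2 is an operative instruction. In cycle 1 of the 5-day cohorts the general rule allows no modification or interruption, so the practical choice is to continue or to stop, and this is the sentence that states the choice for liver tests. Both of its inputs are available while drug is running: the row "Acute Care, Hepatic and Mineral Panels and LDH" in the Section 3.8.2 calendar is marked on each of days 1 to 6, and so is the physical examination. Section 3.2 notes that liver-test rises are seen mostly in the first 7 days of treatment, a window that contains the whole infusion.

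**Working it through.** The plan gives no figure on this point, so the check sets the two sentences side by side.

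**Inputs.** Infusion length is 120 h or 240 h (Section 3.4). The duration limits are < 7 days (sentence 1) and not more than 7 days (sentence 2). For this check the signs in sentence 1 and the findings in sentence 2 are treated as the same thing.

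**Step 1: can the duration limit be passed during infusion?** 120 / 24 = 5 days, which is less than 7. For an abnormality that starts after the infusion begins, the duration condition of sentence 2 is always true while drug is running. To exceed 7 days before the infusion ends, an abnormality would have to start more than 7 − 5 = 2 days before the infusion. For ALT and AST the entry limit of < 2.5 × ULN (Section 2.1.1.8), against a grade 3 threshold of > 5 × ULN (Section 3.2), makes that implausible. The inclusion criteria set no limit for bilirubin or alkaline phosphatase.

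**Step 2: apply both rules.** Exempt = (< 7 days) AND (no signs). Continue = (not > 7 days) OR (no signs). The DLT column assumes a related event in cycle 1.

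| Duration | Signs | Sentence 1 | Sentence 2 as written | Conflict | Sentence 2 with 'and' |
|---|---|---|---|---|---|
| 3 or 5 days | no | exempt | continue | no | continue |
| 3 or 5 days | yes | DLT | continue | **yes** | stop |
| 7 days | no | DLT | continue | yes | continue |
| 7 days | yes | DLT | continue | yes | stop |
| 8 days | no | DLT | continue | yes | stop |
| 8 days | yes | DLT | stop | no | stop |

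**Step 3: read off the open cohorts.** Only the first two rows can occur during a 120-hour infusion when onset is after its start. Sentence 2 continues drug in 2 of 2, sentence 1 makes 1 of 2 a DLT, and 1 of 2 conflicts. With 'and', 0 of 2 conflict. The 7- and 8-day rows matter for dosing only on the 10-day schedule (240 / 24 = 10 days), and 7 days is reached there only if onset falls within the first 10 − 7 = 3 days.

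**Step 4: what 'and' alone leaves.** One row still conflicts: exactly 7 days without signs, because one sentence says < 7 and the other more than 7. Using < 7 in both removes it.

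**Side check on escalation.** The Section 8 table follows from (1 − p)³ + 3p(1 − p)⁵. For p = 10% to 60% this gives .906, .709, .494, .309, .172 and .082, against the printed .91, .71, .49, .31, .17 and .08. It uses only the DLT rate, and sentence 1 decides what is a DLT, so sentence 2 does not enter.

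**The case against.** The best defence is that sentence 2 should not be read apart from sentence 1. Both sit in one bullet of exceptions, and the abnormalities in sentence 2 can be taken to be those already exempt under sentence 1. A patient with hepatic signs would then be outside the bullet, and sentence 2 would only name what ends the exemption. The hematologic exceptions work that way: treatment continues unless signs of significant infection appear. This is good evidence that 'and' was meant. It does not cure the text, because sentence 2 states persistence and hepatic findings as its own conditions and repeats the negation in each half, so it cannot be read as neither/nor.

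The safeguards elsewhere also stand. A related cycle 1 event with signs is a DLT, Section 3.10.1 takes that patient off treatment, and Section 3.5 recognises stopping for safety. Single-institution inpatient care makes a literal misreading less likely. These safeguards limit the consequence, but they also mean that the specific dosing sentence points the opposite way from the general rules.

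Two further objections are fair. The 1 of 2 counts rule combinations, so the ratio depends on which rows are listed and says nothing about patients. And hepatic signs (sentence 1) and findings of hepatic toxicity (sentence 2) need not coincide: fatigue is a listed effect of rhIL-15, so lethargy may not be hepatic. Changing 'or' to 'and' therefore removes the conflict fully only if one term is used in both places.

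**Conclusion.** This is a minor internal contradiction in a dosing rule. Taken literally, sentence 2 continues rhIL-15 despite hepatic signs for any abnormality that starts during a 120-hour infusion, while sentence 1 and Section 3.10.1 lead to stopping when the event is related and in cycle 1. The conclusion assumes onset after the infusion starts and that the two terms for hepatic signs mean the same thing. The mismatch at exactly 7 days is a lesser fault in the same bullet.

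Stronger readings are tempting but not supported:

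- A reader might infer that the protocol leaves a patient with hepatotoxicity without a stopping rule. Sections 3.5 and 3.10.1 provide one.
- A reader might infer that DLT counts or the 5-day MTD are distorted. They are not, because sentence 1 defines the DLT.
- A reader might take the one exception to the absence of clinical hepatotoxicity, mentioned in Section 3.2, as showing that the conflict has already arisen. Its details are not in the available text, and Section 3.2 sets against it the limit on hepatic tumor replacement (30% in Section 2.1.2.4).
- Continuing through asymptomatic grade 3 rises is a deliberate, explained choice and is not in question.

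**What to change.** Reword sentence 2 so that rhIL-15 continues only while the abnormality has lasted < 7 days **and** the patient has none of the clinical signs of hepatic dysfunction listed in sentence 1. This carries over sentence 1's duration limit and its term for signs, so it removes the 'or', the mismatch at exactly 7 days and the difference in terms together.

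Leave the consequences to the existing DLT definition (related, cycle 1) and to Sections 3.5 and 3.10.1. Do not add a mandatory stop for unrelated events or for later cycles: the DLT definition does not reach them, and Section 3.5 leaves early termination in later cycles to judgment for patients with clinical benefit.

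The cost is one sentence in one bullet, by amendment. No patients, visits or procedures are added, and the escalation rules do not change.
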